5.1.3 Phase one

The phase one portion of this trial will be a phase-1 dose escalation to determine the safety of plinabulin in combination with nivolumab. For the initial portion of this phase, 3 patients will be enrolled and will receive plinabulin at a dose of 20 mg/m² as well as nivolumab at 240 mg for 1 cycle. Cycles will consist of plinabulin and nivolumab on days 1 and 15 of a 28 day cycle. After these patients receive at least 1 cycle of treatment, and if no DLTs are seen, another cohort of 3 patients will enroll, and be treated with plinabulin at a dose of 30mg/m² and nivolumab at a dose of 240 mg. If there are no DLTs after the first cycle of treatment, the trial will continue with the second phase of the study. Alternatively, if

one or more patients in either cohort experience a DLT the cohort in question will expand to include a total of 6 patients. If no other DLT are seen in these 6 patients, then the next phase of the study will continue. If two or more (2/6) patients in this cohort experienced a DLT, then will stop and an alternative dose level may be considered after further discussion with the sponsor and analysis of the DLT by the study team. If this were to be the case the protocol will be amended. If a delayed DLT occurs (i.e. a DLT that occurs during cycle 2 of treatment) the DLT evaluation period will be extended to include the first 2 cycles of treatment. For definitions of DLT please see section [7.1](#)

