As monotherapy plinabulin was generally well tolerated. Adverse events (AEs) that occurred in $\geq 20\%$ of patients included nausea (61%), vomiting (47%), diarrhea and fatigue (34% each), constipation, pyrexia, and headache (26% each), anorexia (24%), and anemia (21%). AE of all grades that were possibly related to plinabulin included nausea (53%), vomiting (37%), diarrhea (29%), and fatigue (21%). Overall, 16 (42%) patients experienced serious adverse events (SAEs), the majority of which were considered not related to plinabulin. No cardiac or neurologic side effects were observed. DLTs were not observed in patients treated at 30mg/m² in the dose-escalation portion of the study, however RP2D was determined to be 30 mg/m²

Clinical Study Protocol 9602
Drug Substance: plinabulin
IND: 129799
Protocol v5.1
Date 7/15/2017

based on mechanism-based adverse events and the presence of a biological response on tumor blood flow. While no patient achieved a CR or PR, the proportion of patients with stable disease appeared to increase with increasing plinabulin dose (7/18 (47%) evaluable patients achieved stable disease at the RP2D level).

In the phase 1/2, open label study to evaluate plinabulin in combination with docetaxel in patients with advanced NSCLC that had progressed after treatment with at least 1 chemotherapy regimen (2014 ASCO abstract. J Clin Oncol 32:5s, 2014 (suppl; abstr 8054). On the phase II portion of the study patients were randomized to receive plinabulin (30 mg on days 1 and 8) and docetaxel (75 mg on day 1) vs docetaxel alone. A total of 90 patients received plinabulin plus docetaxel and 73 received docetaxel alone. Plinabulin was found to be generally well tolerated in combination with docetaxel and appeared to have a similar AE profile as single agent docetaxel, although surprisingly the combination had a significantly lower rate of neutropenia (all events and events \geq Grade 3) than patients treated with docetaxel alone ($p \leq 0.01$). Furthermore, the proportion of patients who required G-CSF and the median cycles of G-CSF received, as well as the rate of docetaxel dose reduction, was lower with the combination than with docetaxel alone.

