phase 2 open label study of patients with advanced stage lung cancer treated in the second or third line setting with plinabulin and nivolumab.

Endpoints

5.1.1 Primary endpoints.

- For the initial phase. To determine the safety and tolerability of the combination of nivolumab and plinabulin.
- For the subsequent phase, To evaluate the overall response rate, defined as the sum of complete and partial responses according to RECIST 1.1 criteria, of patients treated with a combination of plinabulin and nivolumab.

5.1.2 Secondary endpoints.

- Evaluate disease control rate, defined as the proportion of patients with CR, PR and SD for more than 8 weeks while on combination plinabulin and nivolumab.
- Evaluate duration of response (DOR), Progression Free Survival (PFS) and Overall Survival (OS)
- Determine the safety and tolerability of the combination of nivolumab and plinabulin.

Dose rationale

Plinabulin has been studied as a single agent in a dose escalation study, the maximum tolerated dose was not reached and the recommended phase 2 dose was 30mg/m². A subsequent phase 1 study using plinabulin with docetaxel showed that plinabulin did not contribute to the toxicity of docetaxel⁹. In this study the initial phase will start with a dose of plinabulin of 20 mg/m² and nivolumab at a flat dose of 240mg. If no dose limiting toxicities (DLTs) are seen the dose of plinabulin will be escalated to 30 mg/m²

Treatment plan

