5.1.4 Second Phase

In the second phase of the study patients will receive plinabulin at the MTD identified previously and nivolumab 240 mg on the same day and repeated every 2 weeks. Re-staging studies will be conducted every 8 (+/-1) weeks, after cycle seven scans will be done every 12 (+/-1) weeks. Those who achieve a complete response, partial response, or stable disease will continue on study. Will use RECIST 1.1 criteria to determine response to treatment. Patients with progressive symptomatology and progressive disease seen in imaging studies will be taken off study. To account for pseudo-progression, in the case of progressive disease in the absence of worsening symptomatology, at the discretion of the treating physician, a patient will be allowed to continue receiving treatment for 2 more cycles followed by restaging studies. If progressive disease is confirmed the patient will be taken off study.

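### Phase 1 expands a cohort to 6 after any number of DLTs in the first 3, so the literal rule enrols more patients at a dose that already meets the stop count of two

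*Combined protocol and SAP*

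**What the plan says.** Phase 1 has two planned cohorts, plinabulin 20 mg/m² and then 30 mg/m², each with nivolumab 240 mg. It opens as follows: "For the initial portion of this phase, 3 patients will be enrolled and will receive plinabulin at a dose of 20" mg/m². Section 5.1.3 then gives these rules.

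- No DLT in the first 3 at 20 mg/m²: open the 30 mg/m² cohort. The dose rationale in section 5.0 has the same condition: "If no dose limiting toxicities (DLTs) are seen the dose of plinabulin will be escalated to 30 mg/m²".
- No DLT in the first 3 at 30 mg/m²: "If there are no DLTs after the first cycle of treatment, the trial will continue with the second phase of the study".
- Expansion: if "one or more patients in either cohort experience a DLT the cohort in question will expand to include a total of 6 patients".
- After expansion, continue: "If no other DLT are seen in these 6 patients, then the next phase of the study will continue".
- After expansion, stop: "If two or more (2/6) patients in this cohort experienced a DLT, then will stop and an alternative dose level may be considered". Sponsor discussion and a protocol amendment follow.

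In phase 2, "patients will receive plinabulin at the MTD identified previously" (section 5.1.4). No separate rule defines the MTD. Section 9.1 applies the Simon design to patients treated at 30 mg/m² or at the MTD.

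**The concern.** The expansion trigger sets a minimum number of DLTs but no maximum. One DLT in three is the result for which three more patients are informative, because the cohort can still finish at 1/6 or reach 2/6. With two or three DLTs in three, the stop count has been met and no result in patients 4 to 6 can bring the cohort back below it. Those patients are exposed without any bearing on the decision.

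Safety and tolerability is the primary objective of phase 1. Under section 7.1 a DLT can be a related Grade 4 non-laboratory toxicity or a Grade 5 event, so the extra exposure is not trivial. Neither the DLT definitions in section 7.1 nor the monitoring plan in section 8.3 holds enrolment at 2/3 or 3/3.

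A smaller question concerns 1/6 at 20 mg/m². The continue sentence covers both cohorts but does not say outright whether this result leads to the 30 mg/m² cohort or to phase 2 at 20 mg/m².

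**Working it through.** **Inputs.** From section 5.1.3: 3 patients at first, expansion to 6 on at least one DLT, stop at two or more. The plan states no target DLT rate and no operating characteristic for phase 1, so there is no figure of its own to reproduce. The true DLT rates q = 0.10, 0.20, 1/3 and 0.50 are assumptions chosen to span a range.

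**Outcome map for one cohort**

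| First 3 | Next 3 | What the text gives |
|---|---|---|
| 0 DLTs | none enrolled | Clear: escalate, or go to phase 2 |
| 1 | 0 | 1/6: continue; destination at 20 mg/m² not stated outright |
| 1 | 1 or more | Stop |
| 2 or 3 | 0 | Expanded although the stop count is met; total 2/6 or 3/6, so stop |
| 2 or 3 | 1 or more | Expanded although the stop count is met; stop |

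The last two rows both end in a stop. The three additional patients change nothing in the dose decision.

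**Formulas**

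- A = P(2 or 3 DLTs in the first 3) = 3q²(1−q) + q³
- B = expected extra patients per cohort = 3 × A
- C = P(at least one further DLT in the extra three) = 1 − (1−q)³
- D = P(1/3 then 0/3) = 3q(1−q)² × (1−q)³ = 3q(1−q)⁵

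At q = 0.10: A = 3(0.01)(0.9) + 0.001 = 0.028; B = 3 × 0.028 = 0.084; C = 1 − 0.9³ = 0.271; D = 3(0.1)(0.9⁵) = 0.177.

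| Assumed q | A | B | C | D |
|---|---|---|---|---|
| 10% | 0.028 | 0.084 | 0.271 | 0.177 |
| 20% | 0.104 | 0.312 | 0.488 | 0.197 |
| 33% | 0.259 | 0.778 | 0.704 | 0.132 |
| 50% | 0.500 | 1.500 | 0.875 | 0.047 |

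**How many cohorts.** Two DLTs at 20 mg/m² stop the trial pending amendment, so the 30 mg/m² cohort does not open. If the 30 mg/m² cohort is open, the 20 mg/m² cohort did not have two DLTs. Under the current protocol at most one cohort, and so at most three patients, can be affected.

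**Where 1/6 at 20 mg/m² leads.** Three places bear on it. Both escalation sentences (5.0 dose rationale and 5.1.3) require no DLTs. The protocol generally uses the word phase for the phase 1 and phase 2 portions and calls the dose groups cohorts, so the next phase most naturally means phase 2. Section 9.1 allows a phase 2 dose other than 30 mg/m². Together these favour phase 2 at 20 mg/m². Column D applies to this result.

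**The case against.** The best defence is that the stop sentence does not say six patients must be treated before it applies, so an investigator who sees two DLTs in three patients would read it as stopping the cohort at once. That is probably what was meant. But expansion is worded as something that will happen, the stop count is given with six as the denominator, and it follows the expansion step. A site following the text is not told to withhold patients 4 to 6.

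A second objection is that the higher assumed rates have no support in the documents. Section 2.0 reports for monotherapy that "DLTs were not observed in patients treated at 30mg/m² in the dose-escalation portion of the study", and gives 7% treatment-related Grade 3 or 4 events with nivolumab in the squamous phase III trial. Neither is a DLT rate for the combination, but both point to the low end, where the expected excess is about 0.08 patients per cohort. This limits the size of the problem but does not remove the defect.

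Three stronger readings are tempting and are not supported.

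- A reader might infer that 2/3 then 0/3 can clear the dose, because no other DLT has occurred. The chance of clearing a dose would then rise from 91% to 93%, 71% to 76%, 43% to 50% and 17% to 23% at the four assumed rates. But that wording naturally presupposes one index DLT, and 2/3 then 0/3 is exactly the 2/6 named in the explicit stop sentence. The increases arise only if a site disregards that sentence.
- A reader might infer that 1/6 at 20 mg/m² has no destination, or that it should lead to 30 mg/m² as in a conventional 3+3 design. The text leans to phase 2 at 20 mg/m², and escalating after a DLT would loosen the stated condition.
- A reader might count three extra patients in each of the two cohorts. Stopping after two DLTs rules that out.

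**Conclusion.** The expansion rule in section 5.1.3 is wrong as written and should be fixed. It enrols up to three patients at a dose that has already met the protocol's stop count, with no possible effect on the decision. The per-cohort chance of this is 3% at a true DLT rate of 10% and 10% at 20%, rising to 26% and 50% at the less plausible rates of 33% and 50%. If it happens, the chance of at least one further DLT among the extra patients is 27%, 49%, 70% and 88%. These figures assume independent patients with a common DLT rate within a cohort and a site that follows the wording literally. The finding itself rests only on the text.

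The final dose decision is not in doubt: two or more DLTs in a cohort mean stop. The destination of 1/6 at 20 mg/m² is a secondary ambiguity. It has probability 18%, 20%, 13% and 5% at the four rates and is most likely where toxicity is low to moderate, so a reassuring safety background does not dispose of it.

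**What to change.** In section 5.1.3:

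1. Make the expansion trigger read: exactly one of the first 3 patients.
2. Add that a second DLT in a cohort, at any time, stops enrolment at that dose at once, followed by the sponsor discussion and amendment already provided for. This also covers a second DLT that appears partway through an expansion.
3. Replace the condition in "If no other DLT are seen in these 6 patients, then the next phase of the study will continue" with: no more than 1 of 6 patients has a DLT.

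As a secondary clarification, state where 1/6 at 20 mg/m² leads. Naming phase 2 at 20 mg/m² would confirm what the text favours. If the sponsor prefers to open the 30 mg/m² cohort after 1/6, that is a deliberate design change: both escalation sentences would have to be amended and the choice justified.

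Items 1 to 3 change wording only and can spare up to three patients. The Simon boundaries and error rates are unaffected.

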5.1.4 Second Phase

In the second phase of the study patients will receive plinabulin at the MTD identified previously and nivolumab 240 mg on the same day and repeated every 2 weeks. Re-staging studies will be conducted every 8 (+/-1) weeks, after cycle seven scans will be done every 12 (+/-1) weeks. Those who achieve a complete response, partial response, or stable disease will continue on study. Will use RECIST 1.1 criteria to determine response to treatment. Patients with progressive symptomatology and progressive disease seen in imaging studies will be taken off study. To account for pseudo-progression, in the case of progressive disease in the absence of worsening symptomatology, at the discretion of the treating physician, a patient will be allowed to continue receiving treatment for 2 more cycles followed by restaging studies. If progressive disease is confirmed the patient will be taken off study.

6.0 STUDY CONDUCT AND TRIAL PROCEDURES

Prior to undergoing any study-specific procedure, patients must read and sign the current Institutional Review Board (IRB)-approved informed consent form. Procedures conducted as part of the subject's routine clinical management (e.g., blood count, imaging study) and obtained prior to signing of informed consent may be utilized for screening or baseline purposes provided these procedures are conducted as specified in the protocol.

Screening

Diagnostic or laboratory studies performed exclusively to determine eligibility for this trial must only be done after obtaining written informed consent. Documentation of the informed consent will be maintained in the patient's chart.

Studies or procedures that were performed per standard of care prior to signing the consent form may be used for baseline values if they fall within the screening specified window (see table 6.10).

The screening visit will occur up to 28 days prior to initiating study treatment. The following should be obtained, [see table 6.10](#).

- Medical History
 - Histologic type of lung cancer diagnosis
 - Prior NSCLC treatment history
 - Medical History
 - Subject demographics
- Physical examination
 - Examination of major organ systems
 - ECOG performance status
 - Height, weight, and vital signs (temperature, blood pressure, heart rate, and respiratory rate),
- Laboratory Evaluations should include:
 - CBC with differential
 - Serum chemistry (sodium, potassium, chloride, carbon dioxide, creatinine, BUN, glucose, calcium, albumin, total bilirubin, AST, ALT, total protein, and alkaline phosphatase)
 - Thyroid function (TSH, T3, Free T4)
 - Pregnancy test (serum or urine) for all women of childbearing potential
- CT scan of known sites of involvement (a prior CT scan that is no more than 28 days before the initiation of treatment may be used).
- Brain MRI or CT (prior MRI or CT scan that is no more than 28 days before the initiation of treatment may be used).

Biopsy

All subjects who sign consent to participate in this trial will undergo a mandatory biopsy prior to the start of treatment and after 1 cycle of treatment. The biopsy is mandatory but the treating physician must deem the biopsy feasible and safe; if the physician feels that the biopsy is not feasible or it is not safe the subject will still be allowed to enroll in trial. The biopsy will take place at baseline after eligibility criteria has been confirmed and after the first cycle. Tumor tissue samples consisting of core needle biopsies of deep tumor tissue or lymph nodes or excisional, incisional, punch, or forceps biopsies of cutaneous, subcutaneous, or mucosal lesions will be obtained. Fine needle aspirates, cell pellets from effusions or bone biopsies are not permitted. Target lesions considered for core needle biopsies should be deemed suitable for retrieval of at least three cores (minimum diameter 18- gauge). The biopsy will be delivered to the laboratory of [name].

Treatment on Days 1 and 15 of each Cycle.

Cycles are defined as 28 days.

- On Days 1 and 15 of each cycle (+/- 2 days), the following will be performed prior to therapy administration:
 - History and physical examination that includes examination of major organ systems, ECOG performance status (Days 1 only), weight (Days 1 only), vital signs, adverse event evaluation
 - Laboratory evaluations (Days 1 only) including:
 - CBC with differential
 - Serum Chemistry (sodium, potassium, chloride, carbon dioxide, creatinine, BUN, glucose, calcium, albumin, bilirubin, AST, ALT, total protein, and alkaline phosphatase)
 - Thyroid function (TSH, T3, Free T4) will be performed on Day 1 of every ODD cycle

Drug Administration

6.1.1 Dose calculation.

Plinabulin doses will be determined by the patient's actual weight on Day 1 of each cycle, Nivolumab doses are fixed at a flat dose of 240mg.

6.1.2 Schedule of administration.

Patients will receive therapy on days 1 and 15 of a 28 day cycle. Therapy will consist of plinabulin administered via intravenous infusion (IV) over 30 minutes (+/- 5 minutes) followed by nivolumab administered via intravenous infusion (IV) over 60 minutes (+/- 10 minutes).

- Cycles one and two require a 1-hr observation period between plinabulin and nivolumab administration. No observation period will be required in subsequent cycles if infusions were tolerated without any infusion reactions.
- Patients will be observed during each infusion and vital signs (blood pressure, heart, and respiratory rate) will be measured prior to (+/- 5 minutes) and at the end of every infusion (+/- 5 minutes).

6.5 Medications

6.5.1 Plinabulin

Plinabulin is an investigational drug that will be supplied by the BeyondSpring.

The clinical formulation of plinabulin will be supplied as a clear solution in amber vials containing 80 mg of drug in 20 mL (4

mg/mL). The correct volume of plinabulin (at a concentration of 4 mg/mL in the vial) is diluted between 1:20 and 1:200 with dextrose 5% in water (D5W) dependent on dose and patient BSA. Prepared dose (approximately 500 mL in DEHP-free bag) will be administered via IV, using standard SCCA infusion tubing¹¹, with an in-line filter peripherally or centrally within 8 hours of dilution. Product must be protected from light at all times (storage, prior to, during and after dilution). Infusion time may be increased as clinically indicated at the direction of the Sponsor.

Source and Product Accountability of Plinabulin

Plinabulin must be stored at room temperature protected from light. Each vial is designated for single use. Vials should be stored upright. The Investigator or designated pharmacist will acknowledge receipt of the shipment and note content and condition of the shipment on the clinical material shipping form. BeyondSpring or its representatives will supply the appropriate forms.

All partially used or empty vial drug counts should be verified by the sponsor's monitor. The site will contact and discuss with the sponsor the method of study drug destruction to determine whether the study drug will be shipped to a designated facility contracted by the sponsor or destroyed at the study center according to the site's Standard Operating Procedures (SOP). If it is determined that the study drug will be destroyed on site, written confirmation of vial destruction and a copy of the institutional SOP must be provided to the Sponsor or its representative.

At the end of the study, all expired or unused medication will be returned to the contract repository with an inventory of returned clinical materials or destroyed on site according to site procedures. BeyondSpring will be notified prior to shipment or destruction.

The pharmacist or person responsible for dispensing the study drug at the site will maintain an accurate and current record of all drug supplies received from the repository and dispensed to the patients. The dispensing record should contain the protocol number and information regarding the amount dispensed; date dispensed, lot #, patient identifier number, patient initials, and the initials of the person dispensing the medication.

6.5.2 Nivolumab

Nivolumab is commercially available. Should be obtained from the institutional pharmacy and prepared per institutional protocol. Please see prescribing information provided by the manufacturer for further details about nivolumab.

6.6 Tumor Evaluations

CT scan of all known areas of disease with tumor evaluation using RECIST 1.1 and IrRC criteria will be performed every 8 (+/-1) weeks. After 7 cycles of therapy, imaging studies will be performed every 12 (+/- 1) weeks.

- Patients who have a CR, PR, or SD may continue on study per study protocol.
- If progressive disease is documented the patient may remain on study provided:
 - The patient does not have clinical signs or symptoms of tumor progression
 - No decline in ECOG performance status
 - Absence of progressive tumor at critical anatomic sites (i.e. spinal cord compression).
 - Treating physician believes that the patient continues to derive clinical benefit from study treatment
 - Repeat imaging scans should be repeated ≥ 4 weeks (+/- 7 days) after documented progression. If progression is confirmed the subject will be removed from study.

Off Study Visit.

Patients will undergo the following assessments 28 days (+/- 14 days) after last dose of study treatment

- History and physical examination that includes examination of major organ systems, ECOG performance status, weight, vital signs, adverse events assessment
- Laboratory evaluations including:
 - CBC with differential
 - Blood chemistry (sodium, potassium, chloride, carbon dioxide, creatinine, BUN, glucose, calcium, albumin, bilirubin, AST, ALT, total protein, and alkaline phosphatase)

Permitted medications

All treatments that the investigator considers necessary for a subject's welfare may be administered at the discretion of the

investigator in keeping with the community standards of medical care.

If an increase in systolic blood pressure to > 160 mmHg is observed after administration of plinabulin, oral amlodipine 10 mg or an equivalent calcium channel blocker should be administered before each subsequent dose. Increases in systolic blood pressure above 200 mmHg should be managed with nitroprusside or similar regimen per institutional practice.

Dexamethasone may be used as either a pre-medication or as a rescue medication for patients that experience plinabulin-related nausea and vomiting that is not controlled adequately with a 5HT3 agonist (e.g. ondansetron) alone

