Patients who discontinue treatment without receiving study medication will be replaced. No other patients will be replaced

Clinical Study Protocol 9602
Drug Substance: plinabulin
IND: 129799
Protocol v5.1
Date 7/15/2017

Schedule of events

	Screening ¹	Cycle 1		Cycle 2+		Off Study ¹²	Survival follow up
		Day 1 +/- 2 days	Day 15 +/- 2 days	Day 1 +/- 2 days	Day 15 +/- 2 days		
Informed consent ²	X						
Demographics	X						
Medical history	X						
Concurrent meds	X	X	X	X	X	X	
Physical exam	X	X	X	X	X	X	
Adverse event evaluation		X	X	X	X	X	X ¹³
Vital signs ³	X	X ¹⁴	X ¹⁴	X ¹⁴	X ¹⁴	X	
Height, weight ⁴	X	X		X		X	
Performance status	X	X		X		X	
Biopsy ⁵	X			X			
CBC w/differential	X	X		X		X	
Serum chemistry ⁶	X	X		X		X	
Thyroid Function ⁷	X	X		X ⁷			
Serum pregnancy test	X ⁸						
Disease assessment (CT scan) ⁹	X			8 (±1) weeks, starting in C7 12 (±1) weeks ¹⁰		X	
Brain CT or MRI	X ¹¹	As clinically indicated					
Survival assessment							X
Plinabulin		X	X	X	X		
Nivolumab		X	X	X	X		

1: screening evaluations must be performed within 28 days of Cycle 1 Day 1
2: consent must be performed prior to initiation of any screening or study-specific procedures

Clinical Study Protocol 9602
Drug Substance: plinabulin
IND: 129799
Protocol v5.1
Date 7/15/2017

- 3: vital signs should include: temperature, blood pressure, heart rate, and respiratory rate
- 4: height is needed at screening only
- 5: biopsy is mandatory for all subjects if treating physician deems it to be safe and feasible. If treating physician deems biopsy not safe and/or not feasible the subject may still be enrolled if they meet all other inclusion criteria.
- 6: sodium, potassium, chloride, carbon dioxide, creatinine, BUN, glucose, calcium, albumin, total bilirubin, AST, ALT, total protein, and alkaline phosphatase
- 7: TSH, T3, Free T4 will be performed at screening and Day 1 of every ODD cycle
- 8: serum pregnancy test (for women of childbearing potential only). Subjects must use an acceptable method of birth control.
- 9: CT scan scan of known sites of involvement. A prior CT scan that is no more than 28 days before the initiation of treatment may be used.
- 10: disease will be assessed 8 (\pm 1) weeks, after cycle 7 patients will be reimaged every 12 (\pm 1) weeks.
- 11: brain CT or MRI does not need to be repeated if scans were performed within 28 days of C1D1
- 12: off-study evaluation will be performed within 28 days (\pm 7 days) after last dose of study treatment

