The study population for analyses will include all patients enrolled in the study who receive treatment at the MTD and receive at least one dose of study medication. The primary endpoint will be overall response rate. As noted above, 11 or more observed responses among 33 patients would be considered potentially efficacious and would justify further study. Responses include both complete and partial responses, as defined by RECIST 1.1 criteria. The disease control rate (DCR), defined as the stable disease + partial response rate will be calculated. Toxicity rates will be described as the overall percentage of patients experiencing Grade 3 or higher toxicity.

9.3 Time to event definitions.

Progression free survival is defined as the time from registration until objective tumor progression or death due to any cause, whichever comes first. The date of disease progression will be defined as the earliest date of radiological disease progression as assessed by the investigator using RECIST 1.1 criteria, or clinical disease progression. For patients who have not progressed or died at the time of the analysis, censoring will be performed using the date of the last adequate disease assessment.

Overall survival is defined as the time from registration until the date of death due to any cause. Patients last known to be alive at the time of the analysis will be censored at the date of last contact.

Duration of response is defined as the time between receipt of first study drug and until the date of progression.

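### Body CT is required only at known disease sites, with no minimum field, so asymptomatic new lesions elsewhere may be missed and the response and progression endpoints mis-measured

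*Combined protocol and SAP*

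**What the plan says.** Three places define the required body CT, all by disease already known:

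- Section 6.0, Screening: "CT scan of known sites of involvement".
- Section 6.6 asks at restaging for a "CT scan of all known areas of disease with tumor evaluation using RECIST 1.1 and IrRC criteria", at 8-week intervals at first and at 12-week intervals after seven cycles.
- Schedule of events, footnote 9, attached to the disease-assessment row: "CT scan scan of known sites of involvement".

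Section 5.1.4 repeats the restaging interval and the use of RECIST 1.1 but says nothing about which regions to scan.

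Brain imaging is handled separately. Screening lists "Brain MRI or CT (prior MRI or CT scan that is no more than 28 days before the initiation of treatment may be used" for every patient; after that the schedule has it "As clinically indicated".

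The phase 2 primary endpoint is CR plus PR by RECIST 1.1 (sections 5.1.1 and 9.2). In section 9.3, PFS runs "until objective tumor progression or death due to any cause"; the date of progression is the earliest radiological progression by RECIST 1.1 as judged by the investigator, or clinical progression.

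**The concern.** RECIST 1.1 builds the overall response from target lesions, non-target lesions and new lesions. A new lesion makes the overall response PD even if the target lesions have shrunk. That component can be assessed only where the scan looks.

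Under the text as written, a patient whose known disease is confined to the chest can be followed by chest CT alone. A silent new liver or adrenal lesion would then go unseen, and a shrinking chest tumor would be recorded as PR. A patient with known abdominal disease would have had the same lesion found. The chance of detecting progression thus depends on baseline spread as well as on treatment effect.

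The trial has one arm and is tested against a fixed 20% response rate, so no concurrent control group is imaged under the same rule.

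**Working it through.** **1. What a compliant scan must cover**

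| Scan | Required coverage | Source |
|---|---|---|
| Baseline body CT | known sites | 6.0 Screening; schedule footnote 9 |
| Restaging body CT | known areas | 6.6; schedule footnote 9 |
| Baseline brain | all patients | 6.0 Screening; schedule |
| Follow-up brain | when clinically indicated | schedule |

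No section adds a minimum field, and none forbids a wider scan. The gap is therefore an asymptomatic new lesion in a region the site was not required to scan.

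**2. Effect by endpoint**

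- ORR: inflated only if the unseen lesion is present by the time the response is recorded. A lesion that appears after an established PR does not remove that PR from best response.
- DCR: inflated if the unseen lesion is present when stable disease or response is recorded.
- DOR and PFS: lengthened if progression is seen late or not at all. For PFS, clinical progression can still supply the event.
- Opposite direction: if a later scan covers more than the baseline scan, a lesion present from the start can look new and be called progression.

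**3. The plan's own design figures**

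Inputs from section 9.1: stop at 4 or fewer responses in 18; otherwise add 15 patients and reject the null at 11 or more in 33; null 20%, alternative 40%.

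- P(early stop | p) = P(Bin(18, p) ≤ 4)
- P(reject | p) = Σ over x = 5 to 18 of P(Bin(18, p) = x) × P(Bin(15, p) ≥ 11 − x)

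| Quantity | Stated | Exact |
|---|---|---|
| Early stop at 20% | 0.72 | 0.716 |
| Early stop at 40% | 0.09 | 0.094 |
| Type I error | .05 | 0.0458 |
| Power at 40% | 0.8 | 0.801 |

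The design reproduces, and no number in section 9.1 is in dispute.

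**4. Sensitivity to misclassified responses (assumed range)**

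Hold the true ORR at 20% and let the apparent ORR be higher because some recorded responders have an unseen new lesion. The implied share of apparent responders is (apparent − 20%) / apparent.

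| Apparent ORR | Share of apparent responders misclassified | P(early stop) | P(reject) |
|---|---|---|---|
| 20% | 0 | 0.716 | 0.046 |
| 21% | 1/21 = 4.8% | 0.678 | 0.062 |
| 22% | 2/22 = 9.1% | 0.639 | 0.082 |
| 23% | 3/23 = 13.0% | 0.599 | 0.106 |

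In patients, three points are 0.03 × 33 = 0.99, or about one expected misclassified patient among 33. One patient can also decide between 4 and 5 of 18, or between 10 and 11 of 33.

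**The case against.** The case against has several parts, and much of it stands.

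- **Wider scanning is allowed.** The text sets what must be scanned and forbids nothing more, and new lesions inside a scanned region would be seen. Section 5.1.4 carries no known-site limit. A reader might infer that new metastases elsewhere are never imaged and that progressed patients are counted as responders. The documents show only that this can happen. Even so, section 5.1.4 sets no field either, so it does not close the gap.
- **Baseline is not confined to known sites in every respect.** Brain MRI or CT is listed for everyone at screening. The limit at baseline applies to body CT.
- **Clinical progression counts for PFS.** History and physical examination take place on Days 1 and 15 of each cycle, so symptomatic progression outside the CT field can be dated between scans. A reader might infer that a missed lesion delays the PFS event by at least one 8- or 12-week interval. That does not follow. The definition of response has no such clinical route, so ORR lacks this safeguard.
- **The error rates say nothing about CT coverage.** Any one- to three-point shift, from whatever cause, gives the same figures, and nothing in the documents supports that range. This is right, and they should be read as sensitivity only.
- **Net bias against the 20% benchmark is unsettled.** The documents do not describe how the historical trials imaged patients, and the opposite error from wider later scans is not quantified. This also stands. It argues for a uniform field, which deals with both directions.

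**Conclusion.** The point holds in a limited form. The required body CT follows known disease at baseline and restaging, with no minimum field. A site in full compliance may therefore miss an asymptomatic new lesion that the named criteria count as progression. This is a stated measurement rule that can distort ORR, DCR, DOR and PFS, with detection that varies between patients. It should be changed, although it does not invalidate the design.

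The size is unknown. The rise in false-positive rate to between 0.062 and 0.106 rests entirely on an assumed shift of one to three points and on every such lesion being present by the time of response. It shows that the rule has little slack (exact type I error 0.0458 against .05). It does not estimate the trial's actual error rate.

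**What to change.** In section 6.0 (Screening), section 6.6 and footnote 9 of the schedule of events, replace the known-site wording with one CT field that applies to every patient at baseline and at each restaging. An example is chest and abdomen including liver and adrenals, plus any other known site. Require the same modality and field throughout, and have section 5.1.4 refer to it. State that overall response is derived from target, non-target and new lesions in that field.

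Follow-up brain imaging can stay as stated. The revision would then leave silent new brain lesions undetected between clinically prompted scans, which the report should acknowledge as a limitation.

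The cost is protocol wording and a longer CT field at an existing visit for patients with chest-only disease. Sample size, decision rule and visit schedule do not change.
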